Appendix 8 Supporting Statistical Documentation

1 MONOTHERAPY DOSE-ESCALATION

This appendix provides details of the design that will guide the monotherapy IV dose-escalation stage of this study and of its operating characteristics through simulations.

1.1 RATIONALE FOR MODEL-BASED DESIGN

The modified Continuous Reassessment Method (mCRM) design uses a statistical model that actively seeks a dose-level close to the maximum tolerated dose (MTD) by using toxicity data from all enrolled evaluable participants to compute a precise dose-toxicity curve. It locates the MTD efficiently and minimizes the number of participants treated at possibly pharmacological inactive dose-levels. Such model-based designs have been successfully applied in many Phase I dose-escalation studies ([Schöffski et al 2004](#); [Le Tourneau et al 2009](#); [Neuenschwander et al 2008](#)). The simulations in this appendix investigate the operating characteristics of the design as implemented for this study.

In this design, the MTD is defined as the dose maximizing the posterior probability that the DLT rate, $\pi(MTD)$, belongs to $[0.2, 0.35]$ while keeping the probability of overdose $P\{p(MTD) > 0.35\}$ below 0.25.

1.2 STATISTICAL MODEL

A two-parameter logistic model with bivariate (log) normal priors will be used to fit the dose-toxicity relationship. The probability of DLT at dose d_j , $p(d_j)$ is defined as

$$p(d_j) = \frac{\exp(\alpha + \beta x_j)}{1 + \exp(\alpha + \beta x_j)}$$

where

$$x_j = \ln\left(\frac{d_j}{d^*}\right)$$

and d^* is the reference dose (in this case $d^* = 100$).

The model thus can be rewritten as:

$$\ln\left(\frac{p(d_j)}{1 - p(d_j)}\right) = \alpha + \beta x_j$$

where α and $\log(\beta)$ are assumed to follow a bivariate normal distribution, $\alpha_0 = \alpha$ and $\alpha_1 = \log(\beta)$ are the parameters to be estimated.

1.2.1 Model Prior

For the multiple participant cohort dose-escalation, the prior distribution will be a mixture of prior informative and minimally informative components. The informative component will be the posterior distribution of the CEA TCB (*cibisatamab*) monotherapy toxicity data (without obitinuzumab pre-treatment), as of cutoff date 20 July 2017, approximated with a bivariate normal distribution. A minimally informative prior «neutral» component will be constructed based on the assumed not toxic and toxic doses. The two components will be mixed in a 10/90% ratio ($p_{i_1} = 0.25$) (informative prior component 10%; minimally informative component 90%).

$$(\alpha, \log(\beta))^T \sim \pi_1 N_1(\mu_1, \sigma_1) + (1-\pi_1) N_2(\mu_2, \sigma_2)$$

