4.3 DOSE JUSTIFICATION

4.3.1 RO7172508

The entry-into-human starting flat dose of 65 μ g was derived from incorporating an integrated approach, which was informed by in vitro activity in high-CEA expressing tumor cells as well as clinical safety experience with *cibisatamab* (see [RO7172508 Investigator's Brochure](#)). Compared to a classical minimum anticipated biological effect level (MABEL) approach, the approach used here reduces the number of participants exposed to sub-therapeutic doses of RO7172508 while ensuring that the starting-dose is in a safe range.

Taking into account 20-fold potency increase, a 400 μ g dose of RO7172508 would be equivalent to 8 mg dose of *cibisatamab* (dose with no relevant cytokine increase documented and no Grade 3-related AEs reported).

Based on the available data, the Sponsor has defined the following intermediate doses in Part I:

- Second cohort: 160 μ g
- Third cohort: 400 μ g
- Fourth cohort: 800 μ g
- Fifth and last cohort: 1.6 mg

Incremental dose-increases may be altered based on emerging PK, PD and safety data but will not exceed 3-fold. If there is no safety concern reported in Part I during the safety

observation period (stopping rule: any RO7172508-related event of Grade ≥ 2 toxicity reported within the DLT window), Part II of the study will start with a dose of 1.6 mg. Dose-escalation for Part II will follow the mCRM-EWOC design (see Section 4.1.2).

A maximum dose of 400 mg Q3W of RO7172508 has been defined. The C_{\max} observed at Cycle 1 of 400 mg (MTD) *cibisatamab* was 113 $\mu\text{g/mL}$. Assuming a potency factor of 20, an equivalent RO7172508 C_{\max} of 5.6 $\mu\text{g/mL}$ is estimated to be achieved by 25 mg. The clinical potency may differ from the in vitro levels; therefore, a maximum dose of 400 mg has been defined to allow this to be tested. The dose-escalation will only take place once a full evaluation of safety data has taken place and the dose-increment levels may be reduced to ensure the participant's safety. Dose-fractionation may also be implemented in Cycle 1 where a dose not exceeding 400 mg will be administered over one cycle e.g., 40 mg on Day 1, 120 mg on Day 8 and 240 mg on Day 15. The maximum SC dose administered QW will be 160 mg QW which is 480 mg over a three-week period/cycle. By applying a conservative bioavailability of $\sim 80\%$ this would equate to 400 mg Q3W IV.

Further details are provided in the [RO7172508 Investigator's Brochure](#).

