1.2.2 Informative Component

The parameters of the informative component are listed below:

$$\mu = (-1.4199504, -0.7110435)$$
$$\Sigma = \begin{pmatrix} 0.173397 & 0.0023933 \\ 0.0023933 & 7.3526064 \times 10^{-4} \end{pmatrix}$$

The minimally informative component makes the design robust against surprising deviations from the informative component.

[figure not shown]
A minimally informative prior component will be constructed based on the assumed not toxic and toxic doses. It is conservatively assumed that would be very unlikely (with a 60% confidence) that 10% or higher DLT rates are associated with the first dose of monotherapy dose-escalation and that it would be very unlikely (with 90% confidence) that a 25% or lower DLT rates are associated with the dose of 400 mg.

The parameters of the minimal informative prior are listed below:

$$\mu = (-0.0983878, -0.4150429)$$
$$\Sigma = \begin{pmatrix} 1.7525039 & -0.0052047 \\ -0.0052047 & 0.0185343 \end{pmatrix}$$

The plot of the prior distribution used for the study can be seen in [Figure 1](#) and it will be the primary prior distribution used to determine the dose-escalation decisions.

Figure 1: Prior Plot

In black the informative, in blue the minimal informative and in red the mixture prior dose-toxicity relationship.

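### The cibisatamab prior component enters the RO7172508 model mg for mg, contradicting the 20-fold potency factor in Section 4.3.1; at 10% weight the effect is moderate

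*Combined protocol and SAP*

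**What the plan says.** Appendix 8, Section 1.2.1 (and Section 4.1.2.2) mixes two bivariate normal components for (alpha, log beta). For the first, "The informative component will be the posterior distribution of the CEA TCB", that is, cibisatamab monotherapy data. Section 1.2.2 prints its mean as the pair "1.4199504, -0.7110435", the first entry carrying a minus sign. The minimally informative component has mean "0.0983878, -0.4150429", again with a leading minus. In Section 1.2 one d* "is the reference dose (in this case" 100) serves both components. The weights are given as "informative prior component 10%; minimally informative component 90" percent, yet the same sentence prints pi_1 = 0.25.

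Section 4.3.1 relates the two drugs twice. "Taking into account 20-fold potency increase", it equates 400 µg of RO7172508 with 8 mg of cibisatamab. Then, "Assuming a potency factor of 20, an equivalent RO7172508" exposure to that at the 400 mg cibisatamab MTD is expected at 25 mg. It adds that clinical potency may not follow the in vitro figure. Section 2.3 says potency was allowed for in the starting dose and does not mention the prior. Appendix 8 contains no potency factor, dose conversion or separate reference dose.

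**The concern.** A dose-toxicity curve borrowed from a less potent drug has to be moved along the dose axis before it describes the new one. If it is not, the component meant to carry in-class toxicity knowledge says that RO7172508 is as toxic per mg as cibisatamab, while the dose justification says it is 20 times as potent. At stake are the 25% overdose limit and the declared MTD in a first-in-human escalation, because Appendix 8 makes this mixture the primary prior for escalation decisions.

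**Working it through.** **Inputs.** Informative mean: alpha = -1.41995, log beta = -0.71104, so beta = exp(-0.71104) = 0.491. Model: logit p(d) = alpha + beta x ln(d/100). Target 20-35%; overdose limit P(p > 0.35) < 0.25. Potency factor 20 and cibisatamab MTD 400 mg from Section 4.3.1.

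**1. Model form.** It reproduces all six target intervals in Appendix 8, Table 2 (for example, 48-75 mg in Scenario 1).

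**2. Scale of the printed curve.**
- 400 mg: -1.420 + 0.491 x ln 4 = -0.739, so p = 32.3%.
- 20 mg: -1.420 + 0.491 x ln 0.2 = -2.210, so p = 9.9%.

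A rate of 32.3% at 400 mg fits cibisatamab's MTD. Had the curve already been converted, that MTD would sit at 400/20 = 20 mg with a 9.9% rate, which does not fit. The match is on the DLT rate only: within the component P(p > 0.35) at 400 mg is 0.39, so 400 mg would not itself pass this study's limit.

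**3. Which scale produced Table 1.** A Monte Carlo rerun (300,000 draws per component, the plan's grid, increment caps and limit) gave:

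| Prior | Cells matched | Of the 8 cells at 40 mg and above with 2-3 DLTs |
|---|---|---|
| Unconverted, 10% | 26 of 36 | 7 |
| Converted x20, 10% | 23 of 36 | 1 |
| Unconverted, 25% | 21 of 36 | 2 |

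Table 1 therefore points to the unconverted component at 10%. Most misses are one grid step; the largest are at 6.4 and 12 mg with 2 DLTs.

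**4. Conversion.** Replacing d by 20d gives alpha_I = -1.420 + 0.491 x ln 20 = -1.420 + 1.471 = +0.05, with log beta unchanged. This equals a reference dose of 100/20 = 5 mg for this component.

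| Dose (mg) | Unconverted | Converted x20 |
|---|---|---|
| 1.6 | 3.1% | 12.1% |
| 20 | 9.9% | 32.3% |
| 25 | 10.9% | 34.8% |
| 100 | 19.5% | 51.3% |
| 400 | 32.3% | 67.5% |

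Section 4.3.1's exposure match implies 400/25 = 16 instead of 20. Then alpha_I = -1.420 + 0.491 x ln 16 = -0.06, and the rate at 25 mg is 32.3%. The conclusion is the same.

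**5. Effect on Table 1 at 10% weight.** After 0 or 1 DLT no next dose changes. Seven cells fall:

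| Dose (mg), DLTs | Unconverted next dose (mg) | Converted next dose (mg) |
|---|---|---|
| 20, 2 | 27 | 25 |
| 40, 2 | 50 | 40-45 |
| 40, 3 | 27 | 25 |
| 80, 2 | 85-90 | 75 |
| 80, 3 | 50 | 45 |
| 150, 2 | 150 | 120 |
| 300, 2 | 250 | 200 |

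Ranges reflect near-ties between numerical methods. A few other cells (12 mg with 2 DLTs, 20 and 150 mg with 3) move down in one rerun but not in another. In five cells (2 DLTs at 40, 80, 150 and 300 mg; 3 DLTs at 80 mg) the unconverted recommendation has 26-29% overdose probability under the converted prior.

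Below 12 mg the change goes the other way: 0.8 to 0.9 mg (1.6 mg, 2 DLTs), 3.2 to 3.6 mg (3.2 mg, 2), 1.2 to 1.3 mg (3.2 mg, 3), 7.8 to 8.3 mg (6.4 mg, 2) and 3.7 to 4.0 mg (6.4 mg, 3). These are rises of about 0.1-0.4 mg (0.5 mg in this rerun for 6.4 mg with 2 DLTs).

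**6. Simulated trials, unconverted to converted.**
- Scenario 1, 250 trials: participants above target 7.2 to 5.8; MTD declared with true rate above 35%, 45% to 31%; MTD in target 38% to 46% (about 1.8 standard errors).
- Scenario 1, 600 trials from 1.6 mg: 6.4 to 5.3; 49% to 37%; 29% to 42%.
- Scenario 1 from Appendix 8's 0.5 mg simulation start: 5.1 to 4.5; 41% to 40%.
- Scenario 4, same start: 3.5 to 2.8 above target, but too-toxic MTDs 29% to 34%.
- True MTD at 15-25 mg: 0.2-0.8 fewer participants above target.

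**The case against.** The best defence is that the plan limits this component by design and declines to rely on the factor. Its weight is 10%. The other 90% reaches 20-35% DLT at 14-46 mg, which brackets the 20-25 mg equivalent dose. Increment caps and clinical override also apply. Section 4.3.1 warns that clinical potency may differ and keeps a 400 mg ceiling so that this can be tested. Scenario 1, which Appendix 8 calls the currently expected toxicity, has its target at 48-75 mg. Its 20% and 35% doses lie 107/48 = 2.2 and 511/75 = 6.8 times below the borrowed curve's, so the sponsor's own expectation is neither 1 nor 20.

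Much of the fall at high doses is also not in-class knowledge regained. Reaching 40-300 mg in the mock runs takes 15-24 participants without a DLT, which already discredits the converted curve. Its posterior weight in the five over-limit cells is 0.5-6%, and dropping the component altogether gives the same or nearly the same dose.

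Below 12 mg conversion loosens control. After 2 of 3 DLTs at 3.2 mg, P(p > 0.35) at that dose drops from 24.5% to 21.5%. Table 1 prints a step down to 3.1 mg; the converted prior steps up to 3.6 mg. A tight component (SD of log beta about 0.027) gains weight after early DLTs and holds down the estimated toxicity.

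All of this limits the harm and shapes the remedy. It does not remove the contradiction: doubt about a factor of 20 is no reason to use a factor of 1 without saying so, and Appendix 8 represents no potency uncertainty.

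**Conclusion.** The inconsistency stands: Appendix 8 uses a potency ratio of 1 and Section 4.3.1 uses 20. At the protocol's own equivalent dose of 20-25 mg the borrowed curve shows 10-11% DLT, where conversion implies 32-35%, about three times as much. In the mixture the effect is moderate and confined to recommendations after 2-3 DLTs, and the gains from conversion vary with scenario and starting dose. It should be fixed but need not hold up the trial.

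A reader might infer that the prior pulls toward safety over the whole escalation range, or that overdose control is broadly compromised. The documents do not support either reading: the low-dose cells move the other way, the component has 10% weight, and the size of the mismatch depends on an in vitro factor that the protocol itself qualifies.

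Assumptions: the component's scale is inferred from its description, the single d* and the fit at 400 mg, since it is not stated; the weight is 10%; the factor is 20. If the weight is really 0.25 the effect grows: too-toxic MTDs in Scenario 1 from 1.6 mg are 58% unconverted against 38% converted.

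**What to change.** 1. State the dose scale of the informative component and put it on the RO7172508 scale before mixing: alpha_I = alpha + beta x ln(factor), about +0.05 for a factor of 20. Use one factor in both Section 4.3.1 and Appendix 8; if it is not 20, say what it is and why.
2. Because the factor is in vitro, add its uncertainty to var(alpha), approximately beta² x var(ln factor), or show results over a stated range of factors.
3. Reconcile the 10% weight with the printed pi_1 = 0.25.
4. Rerun and reissue Tables 1 and 3, showing the cells below 12 mg so that the sponsor can check the model's behaviour after early DLTs.

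The cost is one line of model code, new parameters and two reissued tables. The price in operation is lower model recommendations after DLTs at the higher levels, and slightly higher ones (about 0.1-0.4 mg) after 2-3 DLTs below 12 mg. The second is a real downside and should be stated in the plan.

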4.1.2.2 Part II: Multiple-Ascending Dose-Escalation (Multiple Participant Cohorts)

A modified continual reassessment method with overdose control (mCRM-EWOC) will guide the dose-escalation to determine the MTD, by using primary safety variables (e.g., DLT). This model-based design assigns participants to dose-levels and defines the MTD based on the estimation of the target toxicity level by a model depicting the dose-toxicity relationship. The dose-toxicity relationship is described by a two-parameter logistic regression model, which is continuously updated as additional participant information becomes available.

The prior distribution for the parameters of the DLT dose-response curve will be a mixture of informative and minimally informative components. The minimally informative component makes the design robust against unforeseen deviations from the informative component and will be constructed based on the assumed not toxic and toxic doses. For the dose toxicity relationship of the minimally informative component, it is conservatively assumed that it would be very unlikely that 10% or higher DLT rates are associated with the first dose of the monotherapy dose-escalation and that it would be very unlikely that a 25% or lower DLT rate is associated with a dose of 400 mg (additional details provided in [Appendix 8](#)). The informative component will be the posterior distribution of the CEA TCB (*cibisatamab*) monotherapy toxicity data without obinutuzumab pre-treatment, as of cutoff date 20 July 2017, approximated with a bivariate normal distribution. The two components will be mixed in a 10/90% ratio (informative prior component 10%; minimally informative component 90%). Further details are provided in [Appendix 8](#).

The MTD is defined as the dose with the highest probability that the DLT rate is within the target of 20% to 35%, and a relatively low probability (< 25%) that the DLT rate is above 35%.

- Dose-escalation to IV MTD

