1.4.1 Dose-toxicity Scenarios

In these simulations (Figure 2), the starting dose of 0.5 mg is assumed. Scenario 1 reflects the current expected toxicity of this compound. The others are intermediate or extreme scenarios. The MTD (upper 35% DLT toxicity interval) ranges from 69 mg (low MTD) to 438 mg (illustrating a scenario for which toxicities are expected only at the highest dose).

Figure 2 Dose Toxicity Scenarios

[figure not shown]

Table 2: Scenarios Parameters

Scenario	Target Dose Interval, mg	Parameters
1	48-75	alpha = -0.11, beta = 1.74
2	136-199	alpha = -2, beta = 2
3	247-299	alpha = -5, beta = 4
4	82-121	alpha = -1, beta = 2
5	375-438	alpha = -8, beta = 5
6	23-69	alpha = -0.36, beta = 0.7

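### Appendix 8 gives the cibisatamab prior component two weights, 10% and π₁ = 0.25; at 0.25, ten of 36 model recommendations rise, all past the overdose limit computed with the 10% prior

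*Combined protocol and SAP*

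**What the plan says.** Appendix 8, section 1.2.1 (Model Prior), builds the prior for intercept and log slope from two bivariate normal components. One is informative, taken from cibisatamab monotherapy toxicity data; the other is minimally informative. The weights are given as follows: "The two components will be mixed in a 10/90% ratio ($p_{i_1} = 0.25$) (informative prior component 10%; minimally informative component 90" per cent. The formula beneath multiplies the first component by π₁ and the second by 1 − π₁.

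Protocol section 4.1.2.2 repeats the sentence without the symbol: "The two components will be mixed in a 10/90% ratio (informative prior component 10%; minimally informative component 90" per cent.

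Appendix 8, section 1.2.2, makes this mixture the primary prior for escalation decisions. Section 1.1 defines the MTD as the dose most likely to have a DLT rate of 20% to 35%, "while keeping the probability of overdose" (DLT rate above 35%) below 0.25.

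On dose scale, section 4.3.1 reasons with a potency factor ("Taking into account 20-fold potency increase") and also cautions that "The clinical potency may differ from the in vitro levels". Appendix 8 does not say which assumption the cibisatamab component makes.

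**The concern.** A weight of 10% and π₁ = 0.25 cannot both hold. The first component is not labelled, and I take it to be the informative one from the order of the text. On the reverse reading, 0.25 would conflict with 90% instead, so the contradiction remains.

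Appendix 8 is the specification a programmer would follow, and the symbol in the formula carries the value that disagrees with the words. The cibisatamab component implies low DLT rates at low and middle doses. Extra weight on it makes the model less cautious once DLTs appear, which is where overdose control has to work. If 0.25 were programmed, the overdose probabilities shown at each escalation meeting would be too low relative to the stated prior, and nobody would see it.

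**Working it through.** **Inputs (Appendix 8, sections 1.1 to 1.3)**

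- Model: logit p(d) = α + β·ln(d/100), with (α, log β) drawn from w·N₁ + (1 − w)·N₂.
- N₁ (informative): mean (−1.4199504, −0.7110435); variances 0.173397 and 0.00073526; covariance 0.0023933.
- N₂ (minimally informative): mean (−0.0983878, −0.4150429); variances 1.7525039 and 0.0185343; covariance −0.0052047.
- Printed dose grid; increment cap 100% with no DLT and 50% from the first DLT; cohorts of 3; no DLTs in earlier cohorts.

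**Rule.** The posterior is proportional to [w·N₁ + (1 − w)·N₂] × ∏ pʸ(1 − p)ⁿ⁻ʸ, integrated numerically. Among grid doses within the cap and with P(p > 0.35) < 0.25, take the dose with the largest P(0.20 ≤ p ≤ 0.35).

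**Step 1: reproduce Table 1.**

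| | w = 0.10 | w = 0.25 |
|---|---|---|
| Exact matches | 26/36 | 21/36 |
| Within one grid step | 32/36 | 28/36 |
| Exact at 40 mg and above | 15/16 | 10/16 |

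Five rows match at 0.10 and not at 0.25 (40 mg with 2 and 3 DLTs, 80 mg with 2 and 3, 300 mg with 2). No row does the reverse. The table is not fully reproduced at either weight. The largest misses are 6.4 mg with 2 DLTs (published 6.4; computed 7.8 and 8.2) and 12 mg with 2 DLTs (published 12; computed 15 and 16).

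**Step 2: change the weight.** Ten cells change, all upward. The last column is P(p > 0.35) at the w = 0.25 dose, evaluated under the 10% prior.

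| Current dose, mg / DLTs | Published | w = 0.10 | w = 0.25 | Overdose probability |
|---|---|---|---|---|
| 3.2 / 2 | 3.1 | 3.2 | 3.4 | 0.260 |
| 6.4 / 2 | 6.4 | 7.8 | 8.2 | 0.261 |
| 12 / 2 | 12 | 15 | 16 | 0.2506 |
| 20 / 2 | 25 | 27 | 30 | 0.261 |
| 40 / 2 | 50 | 50 | 60 | 0.302 |
| 40 / 3 | 27 | 27 | 30 | 0.262 |
| 80 / 2 | 90 | 90 | 100 | 0.284 |
| 80 / 3 | 50 | 50 | 55 | 0.265 |
| 150 / 3 | 95 | 90 | 100 | 0.272 |
| 300 / 2 | 250 | 250 | 300 | 0.294 |

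The rises run from 5% (8.2/7.8) to 20% (60/50 and 300/250). The other 26 cells, including every cell with 0 or 1 DLT, do not move.

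**Step 3: simulation.** 1,500 trials per setting with the section 1.2.5 stopping rule; Monte Carlo error about 1.3 points. Trials start at 1.6 mg, not the 0.5 mg stated in section 1.4.1, because a coarser run from 0.5 mg gave mean sample sizes about 3 to 6 above Table 3.

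| Scenario | Mean selected MTD, mg: published / 0.10 / 0.25 | Selected dose has true DLT rate above 35%: 0.10 / 0.25 |
|---|---|---|
| 1 | 72.3 / 69.4 / 80.2 | 44% / 59% |
| 2 | 186.7 / 189.0 / 193.6 | 45% / 48% |
| 4 | 111.7 / 115.0 / 124.5 | 36% / 49% |
| 6 | 45.1 / 47.9 / 54.3 | 21% / 29% |

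The published means lie closer to 0.10 in all four. The published 10–90% quantiles in Scenario 2 (120–250) and Scenario 4 (75–150) equal those at 0.10; at 0.25 they are 150–250 and 85–150.

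**Step 4: dose scale of the informative component (inference).** At the component mean, β = exp(−0.7110435) = 0.49113.

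- At 400 mg: −1.41995 + 0.49113·ln 4 = −0.739, so p = 0.323.
- At 25 mg: −1.41995 − 0.49113·ln 4 = −2.101, so p = 0.109.
- The 20–35% range is 107.1 to 510.8 mg; divided by 20, it is 5.4 to 25.5 mg.

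Section 4.3.1 gives 400 mg as the cibisatamab MTD, so the component appears to be in cibisatamab milligrams with no conversion. The plan also says "Scenario 1 reflects the current expected toxicity of this compound", with a target interval of 48–75 mg, which lies between the two ranges. Rescaling 20-fold at weight 0.10 raises six cells (all at 12 mg or below) and lowers nine (all at 20 mg or above), every one after 2 or 3 DLTs. For example, 6.4 mg with 2 DLTs goes from 7.8 to 8.3, and 80 mg with 2 DLTs from 90 to 75.

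**The case against.** The intended value is hardly in doubt. Section 1.2.1 gives 10% twice in words, section 4.1.2.2 repeats it, and Tables 1 and 3 fit it better. The 0.25 looks like a leftover symbol. That stands, and it is why the correction proposed is 0.10. It does not show what the decision program contains, since mock runs and production code can differ.

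Exceeding the limit is close to automatic. Where the overdose limit already holds the 10% recommendation down, the next higher dose will usually break it. Six of the ten excesses lie between 0.2506 and 0.265, and four published Table 1 doses are themselves at 0.251 to 0.266 by the same calculation. This is fair: the 12 mg case is marginal, and the weight rests on the larger excesses. Five of the ten cells also start from a recalculated dose that differs from the published one; only the five matched at 0.10 in step 1 are anchored to Table 1.

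The simulation percentages depend on detail. The 35% cut-off counts 75 mg in Scenario 1 (true rate 35.2%) and 200 mg in Scenario 2 (35.1%), barely over the line. A coarser 800-trial run gave 52% and 54% in Scenario 1, while a separate 400-trial run gave 43% and 64%, in line with step 3. Scenario 2 shows little effect in any run. The direction is consistent; the exact size is not firm.

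Finally, sponsor and investigators decide each step jointly, and section 4.2.1 lets clinical judgment override the model. That limits the effect, but those decisions would be informed by the misweighted probabilities.

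**Conclusion.** The contradiction is certain: one sentence gives the same prior component weights of 10% and 0.25, and no other text resolves it. The evidence favours 0.10 as the intended value. The harm is conditional. If 0.25 is in the program, ten of 36 recalculated recommendations rise by 5% to 20%, all after at least 2 DLTs in 3 participants, and all exceed the 0.25 overdose limit under the stated prior (0.251 to 0.302). Selection of an MTD with a true DLT rate above 35% would rise most in Scenarios 1 and 4, by roughly 13 to 15 points (59 − 44 and 49 − 36). These results rest on the printed parameters and rules, which reproduce Table 1 closely but not row for row.

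The dose-scale point is secondary. It rests on reading the printed parameters, its effect goes both ways, and the main finding does not depend on it.

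**What to change.** Correct π₁ to 0.10 in Appendix 8, section 1.2.1, and verify that value in the decision program before the next model update. If 0.25 was programmed, rerun Tables 1 and 3 and recheck any recommendation already issued after DLTs. The cost is one symbol and a code check, with reruns only in that case.

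Separately, add a sentence to Appendix 8 reconciling the cibisatamab component's dose scale with section 4.3.1: either state that equal potency per milligram is assumed, or re-express the component. Report Tables 1 and 3 with the component rescaled as a sensitivity run, showing changes in both directions. This costs one sentence and one run of existing code. Adopting a rescaled component would raise some recommendations at 12 mg and below and lower others at 20 mg and above, so that choice stays with the sponsor.
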